Whilst the efficacy of bracing is established, the acceptability of the treatment to adolescents remains unclear. Compliance is a major concern, along with the psychological effects and physical restrictions associated with FTB. Whilst the BrAIST study prescribed FTB for 18 hours a day, the mean compliance was only 12.1 hours per day. Rahimi et al 2019 report a systematic review of brace compliance, noting poor compliance in FTB caused by appearance, comfort and psychological acceptance (6). FTB are worn for an average 46% of prescribed time (range 19-97%) (7).

AIS patients undergoing brace treatment face psychosocial challenges, and there is growing literature to support optimising this aspect of patient care (8,9). A significant proportion of adolescents report a negative psychological impact from the brace, particularly related to the school environment and performing recreational activities (10).

Young AIS patients have never been more exposed to body image influences as a result of social media, which has increased dramatically over the last decade and co tinues at an incline. 69% of 13- to 15-year-olds use Facebook, 66% use Instagram, and 68% use Snapchat in 2019 (11). Teenage girls are also using image-based social media platforms more frequently than their male counterparts. Usage of social media, especially Facebook and Instagram, is associated with body image concerns in young women and men with potential for exposure to bullying (12). Not all social media is negative; there are a number of social media influencers which provide information, support and encouragement for patients with AIS. Involvement of such influencers in this study would both elevate media exposure and even result in a cultural change to have a positive impact on the psychosocial aspect of living with brace for AIS treatment.

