An alternative to the FTB, is a brace only worn at night time (a "night-time brace", or NTB). Such a brace would be 'hidden' from daily life and could significantly improve quality of life and other psychological effects of bracing in this population whilst not increasing the need for surgery. This may therefore have better compliance, with a recent study prescribing a NTB for 8 hours per day and observing a mean wear time of 7.2 hours per day (13). Instead of 'holding' the spine to prevent deformity, these attempt to apply a force to the spine to 'over correct' the deformity. A NTB has several potential advantages over a FTB: (1) curves reduce in size as gravity is eliminated (curves are 10 degrees smaller lying down compared to standing (14)); (2) the brace comes down further over the pelvis than can be achieved for a FTB allowing a longer lever arm and more corrective force applied to the spine, which would make these braces difficult to stand and sit in; (3) the pressure applied to the spine is more constant whilst in bed but tends to reduce over time for braces worn during the day in the upright position (15); and (4) growth occurs mainly at night with higher levels of growth hormone (16).

BASIS Study

The NTB was introduced with the Charleston brace in 1978 (17). This brace is made from a plaster cast model or measurements with the patient laterally flexed towards the side of the curve which produces correction in single curves. However, it is biomechanically less suitable for double curves which limits its use (18) and when double curves are treated in a Charleston brace, success is less than for single curves (19). Low quality comparative studies of Charleston NTB with rigid FTB suggest the Charleston brace may be less effective especially in larger curves (15,16). For these reasons, we will not be using the Charleston brace in this study.

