8.3 Internal pilot outcomes

Criteria are provided below to ensure feasibility of the RCT. Sheffield CTRU will aggregate study data to assess the feasibility of the research and intervention protocols based on the following feasibility outcomes: #At least one NTB/FTB designed, manufactured, fitted and provided to patient

Cross-over will not be assessed within the success criteria as too few patients will have reached the point at which cross-over would be considered (i.e. progression of their condition). Crossover will be monitored by the DMEC.

Domain	Target at end of internal pilot	Green	Amber	Red
Site set-up	19 centres set-up and re- cruited first participant	15 centres re- cruited first par- ticipant	12-14 cen- tres recruited first partici- pant	Fewer than 12 centres recruited first participant
Participant recruitment	Average of 1.1 participants recruited per centre, per month	Minimum 80% of target (per centre per month)	70-79% of target (per centre, per month)	Below 70% of target (per centre, per month)
Retention & cobb angle collection (primary outcome)	gle collection points those randomised col-		70-89% of target	Below 70% of target
Intervention deliv- ery	100% of participants receive the treatment they are ran- domised to [#]	100% of target	85-99% of target	Below 85% of target
Minimum wear time in NTB arm	Participants randomised to do so wear the NTB brace for the prescribed wear time (8-10 hours/day)	Median wear time of at least 7 hours/day	Median wear time of 5-7 hours/day	Median wear time of less than 5 hours/day
Minimum wear time in FTB armParticipants randomised to do so wear the FTB brace for the prescribed wear time (20-23 hours/day)		Median wear time of at least 12 hours/day	Median wear time of 10-12 hours/day	Median wear time of less than 10 hours/day
Compliance data	Compliance data available for 100% of participants who have received a brace and have attended at least one follow-up appointment	Minimum 80% of target	70-79% of target	Below 70% of target

9. Assessments and procedures

All clinical data will be entered by the research site staff onto the British Spine Registry (BSR); PROMs data will also be entered directly onto this system by the patient, with paper copies available if this is not possible. The BSR is an existing national register

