11.1 Sample size

In the BrAIST trial 28% of braced patients progressed to 50 degrees or more before skeletal maturity, which was the primary endpoint (5), so assuming this for the FTB group, with a non-inferiority margin of 11%, 90% power, 2.5% one-sided significance level and 10% attrition, the study will require 780 participants (390 per group).

This margin was chosen based on participants and parents. They have stated there is considerable functional and psychological benefit from not wearing braces during the daytime. During both PPI focus groups patients have expressed mixed views about FTB, which some were being treated with, and the concept of NTB. Approximately 50% of the group expressed a preference for a NTB. In our SAUK survey, 60% said

they would prefer a NTB compared to 27% for a FTB (and 7% no brace, 6% no answer).

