11.2 Statistical Analysis

The trial will be analysed and reported according to CONSORT guidelines for noninferiority designs (54).

The ITT population (and safety) populations will consist of all participants who consent and are randomised to receive FTB or NTB.

The per protocol (PP) will be defined for participants in the FTB group, as

receiving the FTB treatment as documented in the study protocol (see Section 6)
 Complying and adhering to the treatment they were assigned to. Compliance with FTB would mean wearing the brace for average of >12.9hrs/day (= >65% of the minimum prescribed time) over the post-randomisation follow-up period.

For the NTB group, the PP population will be defined as

1) receiving the NTB treatment as documented in the study protocol

2) Complying and adhering to the treatment they were assigned to. Compliance with NTB would mean wearing the brace for average of >5.2hrs/day (= >65% of the minimum prescribed time) over the post-randomisation follow-up period.

Patients who cross-over from NTB to FTB will be removed from the PP population for the analysis of the primary outcome.

The binary primary outcome is curve progression to 50 degrees or more (treatment failure) before skeletal maturity and skeletal maturity without this degree of curve progression (treatment success). Non-inferiority for the primary outcome will be declared if the two-sided 95% confidence interval (equivalent to a one-sided 97.5%) for the risk difference in the event rate of progression to 50 degrees between the NTB group and the FTB group does not exceed 11%. The analysis will be completed using a Generalized Linear Model (GLM) with binomially distributed response and identity link (55) adjusted for baseline covariates (site, skeletal maturity Risser score 0, 1 or 2, and Cobb angle). This will be conducted on both an intention-to-treat (ITT) population and per protocol (PP) basis. The adjusted differences in failure rates, along with 95% con-fidence intervals will be calculated and presented.

Missing data

For the primary outcome, curve progression to 50 degrees or more (treatment failure) and skeletal maturity without this degree of curve progression (treatment success) any missing outcome data will be imputed through a default "worst" case scenario (i.e. assume treatment failure) and "best" case scenario (i.e. assume treatment success) and the results compared with the available data analysis.

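### The binary per-protocol comparison selects on brace wear, unequally between arms and without the weighting planned for the time-to-event version, so its risk difference is open to selection bias and has less power than the ITT analysis

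*Protocol*

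**What the plan says.** Section 11.2 fits a binomial GLM with identity link to failure by skeletal maturity. It adjusts for site, Risser score and Cobb angle, and judges the 95% confidence interval for the risk difference against 11%. On populations it says: "This will be conducted on both an intention-to-treat (ITT) population and per protocol (PP) basis".

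PP membership requires the allocated brace and a minimum average wear over follow-up after randomisation. For FTB the threshold is 12.9 h/day. For NTB: "Compliance with NTB would mean wearing the brace for average of >5.2hrs/day (= >65% of the minimum prescribed time". Participants who cross over from NTB to FTB are also removed from the PP population for the primary outcome.

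The Background (2.1) gives three wear figures:
- FTB in the earlier randomised bracing trial, on an 18 h prescription: "the mean compliance was only 12.1 hours per day".
- FTB in a review: "FTB are worn for an average 46% of prescribed time (range 19-97" (per cent).
- NTB in a recent cohort, on an 8 h prescription: "observing a mean wear time of 7.2 hours per day".

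The internal pilot (8.3) rates FTB wear green from "Median wear time of at least 12 hours/day", and NTB wear green from a median of 7 h.

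Section 11.1 sizes the trial with an 11% margin and "90% power, 2.5% one-sided significance level and 10% attrition". It makes no allowance for PP exclusions.

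Later in 11.2 a time-to-event PP analysis of the same outcome censors non-adherers and uses IPW. The stated reason is that non-adherence may be tied to prognosis, so that censoring could cause selection bias. IPW is also planned for the cross-over analysis. It is not stated for the binary PP analysis.

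**The concern.** The binary PP analysis drops people for behaviour after randomisation, and the two cut-offs sit differently against expected wear. The FTB threshold lies close to or above the expected FTB mean; the NTB threshold lies well below the expected NTB mean. The comparison then sets the better adherers in one arm against most of the other arm. Three baseline covariates cannot be relied on to remove that imbalance, and the protocol recognises the mechanism when it turns to the time-to-event analysis.

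Two forces act. Keeping only the better FTB adherers tends to lower FTB failure in the PP set and so works against NTB. Removing NTB participants who switch, some of whom may be switching because their curve is progressing, may lower NTB failure and work the other way. The protocol gives no cross-over rate, so the net bias cannot be signed.

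In a non-inferiority trial the PP result is read beside ITT. If the two differ, a reader could not tell a treatment effect from selection or from lost precision.

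**Working it through.** **1. Reproduce the stated sample size.** Inputs from 11.1: 28% failure in FTB, margin 0.11, one-sided 2.5%, 90% power, 10% attrition. Assumption: 28% in NTB as well, which is the value that returns the stated size.

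n per arm = 2 × 0.28 × 0.72 × (1.960 + 1.282)² / 0.11² = 350.1, so 351. Then 351 / 0.90 = 390 per arm, 780 in total, as stated. With 351 per arm, SE = √(0.2016 × 2/351) = 0.0339 and power = Φ(0.11/0.0339 − 1.96) = 90.1%.

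**2. Expected FTB wear under the trial's prescription (20 h minimum, section 6.2).**
- Earlier trial, unscaled: 12.1 h.
- Earlier trial, scaled: 12.1/18 = 67%; 67% of 20 h = 13.4 h.
- Review: 46% of 20 h = 9.2 h.

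**3. Share retained.** Share = P(wear > cut-off), taking wear as normal. The protocol gives no SDs; I assume 4-6 h for FTB and 1.5-2.5 h for NTB.

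| Arm | Mean wear | Cut-off | Retained | Of 351 |
|---|---|---|---|---|
| FTB | 12.1 h | 12.9 h | 42-45% | 148-157 |
| FTB | 13.4 h | 12.9 h | 53-55% | 187-193 |
| FTB | 9.2 h | 12.9 h | 18-27% | 62-94 |
| NTB | 7.2 h | 5.2 h | 79-91% | 277-319 |

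With wider SDs (FTB 3-7 h, NTB 1-3 h), retention is 40-46% for FTB at 12.1 h, 11-30% for FTB at 9.2 h, and 75-98% for NTB. NTB shares are before cross-overs are removed. (65% of 20 h is 13.0 h, whereas 11.2 prints 12.9 h; I use 12.9 h. The two should be reconciled.)

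**4. PP power with 28% failure in both arms.** Power = Φ(0.11/SE − 1.96), SE = √[0.2016 × (1/n_FTB + 1/n_NTB)].

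| Mean FTB wear | PP power |
|---|---|
| 12.1 h | 67-71% |
| 13.4 h | 74-77% |
| 9.2 h | 42-55% |

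Example: 148 FTB and 277 NTB give SE = 0.0458 and power 67%.

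**5. A bound that needs no SD.** If FTB median wear is exactly 12 h, the green threshold, at least half of FTB fall below 12.9 h and at most 175 of 351 enter the PP set. With all 351 NTB participants kept, SE = 0.0415 and power is at most 75% at 28% risk.

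**6. Sensitivity to the failure rate.** With 150 FTB and 294 NTB, power is 68% at 28% failure in both arms, 78% at 20% and 87% at 15%.

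**7. Sensitivity to selection (illustrative rates, not from the protocol).** Suppose there is no ITT difference, but retained FTB fail at 25% and retained NTB at 28%. PP power is then 49% with 50%/90% retained and 43% with 40%/85% retained.

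**The case against.** **The protocol does not claim 90% power for PP.** Correct. A reader might infer that the plan misstates PP power, but 11.1 gives one study-level figure, and lower power in a PP companion analysis is usual. Nor does 11.2 say that both populations must meet 11%.

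**IPW is already planned, and a SAP may add detail.** Partly right. The weighted analysis is for time to event. For the binary risk difference, to which the margin applies, the protocol already fixes the population, the cut-offs and a covariate set without weighting.

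**The wear figures are a pessimistic choice.** Partly right. The 12.1 h mean came from an 18 h prescription; scaled to 20 h it exceeds 12.9 h and a little over half of FTB are retained. The green value is a minimum, not a forecast. The imbalance between arms remains in every case shown. It would be wrong, though, to say that almost all NTB participants stay in: a fifth to a quarter could be excluded.

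**Power depends on the failure rate.** It does, and it largely recovers if compliers in both arms fail at about 15%. A far lower figure, about 11%, follows from 20% failure in retained FTB against 28% in NTB, but no source in the protocol supports that split.

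**ITT and PP may well agree.** A reader might infer that disagreement is likely. That is not shown: simulating equal 28% risks with PP nested in ITT gives disagreement in 23% of trials (150 FTB, 294 NTB), 17% (189, 294) and 43% (80, 294).

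**The bias may be conservative.** Selection of FTB adherers does work against NTB, but the cross-over removal may offset it by an unknown amount.

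**Conclusion.** The point stands as a should-fix. The binary PP risk difference rests on unequal selection after randomisation, roughly 45-60% of FTB against 10-25% of NTB, with baseline adjustment only, while the protocol plans weighting against this bias elsewhere for the same outcome. The direction of the net bias is unknown. At 28% failure in both arms, PP power is about 67-77% for mean FTB wear of 12.1-13.4 h and 42-55% for 9.2 h, against 90% for the full evaluable sample; it would be higher if compliers fail less often.

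The retention and power ranges rest on normal wear and assumed SDs. The imbalance itself rests on the protocol's own means, and the 75% ceiling needs only a 12 h FTB median and 28% risk. ITT is unaffected. The documents do not support reading this as a false power statement or as a flaw that undermines the trial's main analysis.

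**What to change.** In 11.2:
- Estimate the PP risk difference at skeletal maturity with the IPW approach already planned for the time-to-event PP analysis, using the non-adherence definition that the protocol says will be pre-specified.
- State that this weighted estimate is the one read beside ITT for the 11% margin.
- Keep the unweighted PP subset as a supporting, descriptive analysis.

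In 11.1:
- State that 90% power refers to ITT with 28% failure in both arms.
- Give the lower PP power over a range of retention in each arm.

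Settle this before the statisticians are unblinded at database freeze (4.1). The cost is wording and extra analysis work, possibly wider intervals from the weights, and a less favourable stated PP power. No extra participants are needed. Weighting addresses the bias; it does not restore the lost power.

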6.5 Other Treatments

Patients will we allowed to have other care such as physiotherapy but this will be recorded. Surgical treatment will not be offered unless the curve gets to 50 degrees as determined by the Radiographic Adjudication Committee (RAC).

7. Randomisation and enrolment

Once eligibility has been confirmed, consent acquired and baseline data taken the participant will be randomly allocated to either the treatment arm (NTB) or the control arm (FTB) on a 1:1 basis, using a web-based system provided by the Sheffield Clinical

Trials Research Unit (CTRU). Patient details (ID, date of birth and stratification information) will be entered into the randomisation system and the treatment allocation will be returned. Randomisation will be completed using minimisation based on site, skeletal maturity (Risser score 0, 1 or 2, and curve size (20-30, 31-40 degrees). Randomisation will be done by site staff. Patients and their parents will be informed of their trial allocation, confirmed by SMS or email, followed by a letter. Their GP will also be informed of their participation in the trial, and their treatment allocation.

8. Outcomes

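### With similar attrition in both arms, the 'worst' and 'best' case imputations both pull the risk difference towards zero, so they favour non-inferiority when night-time bracing is observed to do worse

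*Protocol*

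**What the plan says.** Protocol section 11.1 plans the trial "with a non-inferiority margin of 11%, 90% power, 2.5% one-sided significance level and 10% attrition", takes 28% failure on FTB from an earlier bracing trial, and concludes that "the study will require 780 participants (390 per group"). No split of the 10% attrition by arm is given.

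Section 11.2 declares non-inferiority if the two-sided 95% confidence interval "for the risk difference in the event rate of progression to 50 degrees between the NTB group and the FTB group does not exceed 11" per cent. The estimate comes from a covariate-adjusted binomial model with identity link, run on the intention-to-treat and per-protocol populations.

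Under the missing-data heading of the same section, a missing primary outcome is to be "imputed through a default 'worst' case scenario (i.e. assume treatment failure) and 'best' case scenario (i.e. assume treatment success"). Both runs then serve as a check on the analysis of observed outcomes, since the plan wants "the results compared with the available data analysis". Nothing ties either scenario to one arm, so as written each applies to both. The protocol states no arm-specific, delta-adjusted or tipping-point scenario.

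**The concern.** The usual reason for an all-failure and an all-success run is to show that the conclusion survives pessimistic and optimistic guesses about the patients who were lost. Giving the same outcome to the missing patients in both arms dilutes the contrast between the arms. In a superiority trial that dilution works against the claim. In a non-inferiority trial it works for the claim whenever the new treatment is observed to do worse, which is the situation in which a robustness check matters most. The labels add to the problem: 'worst' here means worst for patients overall, not worst for the hypothesis under test.

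At stake is how the result is read. A reader who sees both scenarios fall below 11% may conclude that missing data cannot explain the finding, although the threatening pattern was never tried. That pattern is plausible. Patients and treating clinicians are unblinded (section 4.1), patients are allowed to switch from NTB to FTB but not the reverse (section 6.4), and section 11.2 itself says that non-adherence might be related to prognosis. Patients lost from the two arms could differ in prognosis even if their numbers match.

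**Working it through.** **Inputs.** FTB failure 28%, margin 11 points, one-sided 2.5%, power 90%, attrition 10%, 390 per arm (section 11.1); 1:1 allocation (section 7). The split of missing data by arm is an assumption: equal at 10% first, then unequal. All limits below are unadjusted Wald limits; the planned adjusted model would shift them slightly.

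**The plan's own figure.** n = (1.960 + 1.282)² × 2 × 0.28 × 0.72 / 0.11² = 350.1, so 351 per arm. Then 351 / 0.90 = 390 per arm, 780 in total. This matches.

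**General form.** Let p be the observed failure rate, m the missing share and q the failure rate assigned to missing patients, by arm:

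RD' = [(1 - mN)pN + mN·qN] - [(1 - mF)pF + mF·qF].

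With mN = mF = m this becomes RD' = (1 - m)(pN - pF) + m(qN - qF). The 'worst' case sets qN = qF = 1 and the 'best' case sets qN = qF = 0. In both, qN - qF = 0, so RD' = (1 - m)RD. The denominator also rises from 351 to 390.

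**Equal attrition, 28% v 32.5%, m = 0.10.**

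| Analysis | FTB | NTB | RD | Upper limit |
|---|---|---|---|---|
| Available data (351/arm) | 28.0% | 32.5% | 4.50 | 11.29 (fails) |
| 'Best' (390/arm) | 25.2% | 29.25% | 4.05 | 10.29 (passes) |
| 'Worst' (390/arm) | 35.2% | 39.25% | 4.05 | 10.83 (passes) |
| Missing NTB fail, missing FTB succeed | 25.2% | 39.25% | 14.05 | 20.53 |

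First row: SE = √[(0.28 × 0.72 + 0.325 × 0.675)/351] = 0.0346, and 4.50 + 1.96 × 3.46 = 11.29.

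**How wide the band is.** With 98/351 FTB failures and 39 missing per arm:

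| NTB failures (of 351) | Available-data upper limit | 'Worst' | 'Best' |
|---|---|---|---|
| 112 | 10.76 | 10.36 | 9.81 |
| 113 | 11.05 | 10.62 | 10.08 |
| 114 | 11.34 | 10.88 | 10.34 |
| 115 | 11.64 | 11.14 | 10.60 |
| 116 | 11.93 | 11.40 | 10.87 |
| 117 | 12.22 | 11.66 | 11.13 |

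Both imputations turn a failure into a pass at 113 and 114, only 'best' does so at 115 and 116, and neither does from 117.

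**Unequal attrition.** One scenario then moves towards the margin.
- NTB 13%, FTB 7% missing (95/339 v 102/363): available-data upper limit 6.58. All-failure gives (95 + 51)/390 - (102 + 27)/390 = 4.36, upper limit 11.06 (fails). All-success gives 4.30.
- NTB 7%, FTB 13% missing (116/363 v 95/339): available-data upper limit 10.70. All-success gives 116/390 - 95/390 = 5.38, upper limit 11.61 (fails). All-failure gives 6.01.

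**What a graded check would show.** Take 105/351 NTB and 98/351 FTB failures: RD 1.99, upper limit 8.70, a pass. The same-direction scenarios give 8.53 ('worst') and 7.95 ('best'). Now let 11 of the 39 missing FTB patients fail (28%). With 21 of the 39 missing NTB patients failing, RD = 126/390 - 109/390 = 4.36, upper limit 10.79. With 22 failing (56%), RD = 127/390 - 109/390 = 4.62, SE = 3.29, upper limit 11.05. The conclusion turns at about 56% failure among missing NTB patients against 28% among missing FTB patients. The two stated scenarios do not show this.

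**The case against.** The strongest reply has four parts.

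**The pair can challenge the claim.** A reader might infer that neither scenario could ever count against non-inferiority. The unequal-attrition cases above show otherwise, and unequal attrition is plausible in an unblinded trial whose background section describes poor compliance with FTB. If NTB is observed to do better, shrinkage even moves slightly against it: at an observed difference of -4.0 the all-failure upper limit is 3.02 against 2.49. This part stands, but the challenge then depends on how many patients happen to be lost from each arm, not on how they might have fared.

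**The decision is not taken on imputed data.** A reader might infer that the trial's error rate is inflated. At a true 11-point difference with exactly 39 missing per arm, the upper limit falls below 11% in 2.5% of trials on available data, 3.6% under 'worst' and 4.8% under 'best'. The imputed figures would be trial error rates only if an imputed analysis decided the result. The protocol says only that these results are compared with the available-data analysis. Available data fail while both imputations pass in about 1.1% of such trials. This part stands.

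**Other analyses exist.** Section 11.2 also plans a per-protocol analysis, time-to-event analyses that can use partial follow-up, and a mixed model for Cobb angle. Section 9.6 asks withdrawing patients to allow routine data to inform the primary outcome. So the pair is not the only robustness evidence. But the weighting and structural failure time methods address non-adherence and switching, and no stated analysis varies the missing primary outcomes by arm.

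**Detail is left to the analysis plan.** That plan is not shown and may add more. The protocol nevertheless fixes these two scenarios as its default, so this is a stated choice and not an omission.

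**Conclusion.** The point holds for similar attrition in the two arms, which is the natural reading of a single 10% allowance with 390 per arm. Both scenarios then shrink the risk difference by exactly (1 - m), that is by 10% of its value at the planned attrition. When NTB is observed worse they lower the upper limit: by about 0.5 ('worst') to 1.0 ('best') percentage points in the 28% v 32.5% example. That is enough to turn a failed result into a pass in a narrow band, at observed differences of about 4.3 to 4.6 points for both scenarios and up to about 5.1 for 'best' alone.

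The documents do not support reading this as a general masking of failure, as a flaw in the primary estimator or decision rule, or as inflation of the trial's type I error. The weakness is confined to the stated missing-data check: it does not test the pattern that would threaten the claim, and where arms lose similar numbers it leans towards the claim. It should be corrected before unblinded analysis. The figures rest on unadjusted Wald limits, 28% FTB failure and the attrition splits shown.

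**What to change.** Keep the available-data analysis as the basis for the decision. Add a tipping-point analysis of the primary outcome in which the failure probability of missing patients varies separately by arm, up to missing NTB all failing and missing FTB all succeeding, and report the combinations at which the upper limit crosses 11%. The grid may be anchored on imputation by arm from the Cobb angle, Risser stage and sensor wear time already collected.

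The arm-opposed extreme should not be used alone. With 39 missing per arm it gives an upper limit of 16.4 at an observed difference of zero, and 12.7 even when NTB is observed 4 points better, so it would defeat almost any result. The informative output is where the limit is crossed and whether that combination is clinically credible.

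If the two same-direction scenarios are kept, state beside them that with similar attrition they favour non-inferiority when NTB is observed worse, and report the number missing by arm. The cost is a few sentences in the protocol or analysis plan and one extra table; no additional data are needed.
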